1.2. Study Design

Overview of Study Design and Key Features	

The diagram illustrates the study timeline. It is divided into three main phases: 'Screening Covid-19 patients', 'Assessments as detailed in Schedule of Activities', and 'Follow-up'. The 'Screening' phase is indicated by a dotted line and a box labeled '548 hours'. This leads to a 'Randomization IV infusion' box, which branches into two treatment arms: 'Otilimab 90 mg' and 'Placebo'. Below this, a long horizontal bar represents the 'Standard of Care (per institutional protocols)'. The 'Assessments' phase includes a 'Day 28 Primary endpoint' box. The 'Follow-up' phase includes 'Day 42 FU assessment Phone call if discharged' and 'Day 60 FU assessment Phone call if discharged' boxes.
	
Design Features	
This study is a multi-center, randomized, double-blind, placebo-controlled trial to assess the efficacy and safety of otilimab for the treatment of severe pulmonary COVID-19 related disease. The study population consists of hospitalized participants with new onset hypoxia requiring significant oxygen support or requiring early invasive mechanical ventilation (≤ 48 hours before dosing). All participants will receive standard of care as per institutional protocols, in addition to study treatment.

Study intervention	
Otilimab 90mg or Placebo, single intravenous infusion

Study intervention Assignment	
Participants will be randomized 1:1 by interactive response technology (IRT) in a blinded manner to receive either a blinded 1-hour infusion of otilimab 90mg or placebo IV in addition to standard of care. Participants will be assessed daily until discharge from investigator site (or Day 28, whichever is sooner), and followed up at Days 42 and 60 after randomization.
 
Stratification in Part 1 – based on the study eligibility criteria, the clinical status of the participants entering the main cohort (i.e. after the 20th participant) of the study will be within ordinal scale categories (5 or 6) and also age groups, as shown below.
 
 • CCI [redacted] Age <60 years • CCI [redacted] . Age 60 to <70 years • CCI [redacted] . Age 70 to <80 years • CCI [redacted] . Age <60 years • CCI [redacted] . Age 60 to <70 years • CCI [redacted] . Age 70 to <80 years

	
Stratification in Part 2 – Based on the study eligibility criteria, the clinical status of the participants entering Part 2 of the study will be within the two ordinal scale categories 5 and 6 and also sex, as follows:
 
• CCI [REDACTED] [REDACTED]. Male• CCI [REDACTED] [REDACTED]. Female• CCI [REDACTED] Male• [REDACTED] Female
--	--

2. STATISTICAL HYPOTHESES / SUCCESS CRITERIA

The primary objective of Part 2 of this study is to compare the efficacy of otilimab 90 mg IV versus placebo in age 70 and above years old participants with severe pulmonary COVID-19 related disease.

Part 2 of the study will test the null hypothesis that there is no difference (odds ratio = 1) between otilimab 90 mg and placebo on the proportion of participants alive and free of respiratory failure at Day 28 versus the alternative hypothesis that there is a difference (odds ratio \neq 1). The primary endpoint and all secondary and exploratory endpoints will be conducted using a two-sided test at the 5% significance level.

2.1. Multiple Comparisons and Multiplicity

The testing of secondary endpoints will be carried out sequentially according to the following hierarchy, significance can only be claimed only if the current test and all prior tests are significant.

1. Participants alive and free of respiratory failure at Day 60
2. All-cause mortality at Day 28
3. All-cause mortality at Day 60
4. Time to recovery from respiratory failure up to Day 28
5. Time to final ICU discharge up to Day 28

3. ANALYSIS SETS

Analysis Set	Definition / Criteria	Analyses Evaluated
Screened	
 All participants who were screened for eligibility 	
 Study Population
Enrolled	
 All participants who entered the study. Data should be reported according to the randomised treatment Note: screening failures are excluded from the enrolled analysis set as they did not enter the study. 	
 Study Population
Safety	
 All participants who received study intervention. Data should be reported according to the actual treatment received 
 If participants receive any Otilimab then they will be summarised according to "Otilimab 90mg", including interrupted/incomplete infusion. 	
 Safety Study Population
Modified Intent-To-Treat (MITT)	
 All randomized participants who received study intervention Data should be reported according to the randomised treatment 	
 Efficacy
Pharmacokinetic (PK)	
 All participants in the Safety analysis set who had at least 1 non-missing PK assessment (Non-quantifiable [NQ] values will be considered as non-missing values). Data should be reported according to the actual treatment 
 If participants receive any Otilimab then they will be summarised according to "Otilimab 90mg", including interrupted/incomplete infusion. 	
 PK

3.1. Protocol Deviations

Important protocol deviations (including deviations related to study inclusion/exclusion criteria, conduct of the trial, patient management or patient assessment) will be summarised.

Protocol deviations will be tracked by the study team throughout the conduct of the study. These protocol deviations will be reviewed to identify those considered as important as follows:

- Data will be reviewed prior to freezing the database to ensure all important deviations are captured and categorised in the protocol deviations SDTM dataset.
- This dataset will be the basis for the summaries of important protocol deviations.

A separate listing of all inclusion/exclusion criteria deviations will also be provided. This listing will be based on data as recorded on the inclusion/exclusion page of the eCRF.

4. STATISTICAL ANALYSES

4.1. General Considerations

4.1.1. General Methodology

The study population analyses will be based on the “Enrolled”, “Screened” or “Safety” populations. The MITT Analysis Set will be used for all Efficacy analyses, and Safety Analysis Set will be used for all safety analyses, unless otherwise specified.

In the case of a difference between the stratification assigned at the time of randomization and the data collected in the eCRF:

- subgroups will be summarised based on the actual subgroup to which the participant belongs
- covariate adjustment will be based on the randomised strata

In general, all analyses will be adjusted for treatment, clinical status at Baseline, sex (male or female), age (as a continuous variable), baseline of the variable of interest (if appropriate) unless otherwise stated. If the number of participants is small within a category of a covariate, then the covariate categories may be refined. If the category cannot be refined further, then the covariate may be included as a continuous measure. If a covariate is highly or perfectly correlated with a subgroup/population, e.g. ICU Status and clinical status at Baseline, then covariates may be removed. Confidence intervals will use the 95% levels unless otherwise specified.

Unless otherwise specified, continuous data will be summarized using descriptive statistics: n, mean, standard deviation, median, minimum and maximum. Categorical data will be summarized as the number and percentage of participants in each category.

Visit windows will be applied to the analysis days, where data within the window of the target day may be used if data is not recorded on the actual day. See Section 6.3.1 for assessment windows.

4.1.2. Baseline Definition

For all treated participants, for all endpoints and measurements the baseline value will be the latest pre-dose assessment with a non-missing value, including those from unscheduled visits. If time is not collected, Day 1 assessments that were noted to be pre-

dose per the Schedule of Activities are assumed to be taken prior to first dose and used as baseline.

For all participants randomized but not dosed, for all endpoints and measurements the baseline value will be the latest assessment on or prior to the date of randomization with a non-missing value, including those from unscheduled visits.

For ventilation status, baseline ventilation status will be derived as the ventilation at the time of dosing, and if there are multiple ventilation types being used the worst case will be assumed.

Unless otherwise stated, if baseline data is missing no derivation will be performed and baseline will be set to missing.

4.1.3. Multicenter Studies

It is anticipated that patient accrual will be spread thinly across centers and summaries of data by center would unlikely be informative and will not, therefore, be provided.

4.1.4. Intercurrent Events

In general, the following may be considered intercurrent events (ICEs) if not part of the endpoint definition:

- Interruption or infusion stopped early and not completed
- Incorrect study treatment administered
- Use of additional medications or changes to standard of care
- Death
- Initiation of Invasive Mechanical Ventilation
- Extubation following Invasive Mechanical Ventilation
- Independence from supplementary oxygen
- Discharge from investigator site

The applicable intercurrent events for each endpoint will be highlighted within in the endpoint definition along with the strategy for handling them.

In general, unless otherwise specified, the handling strategy for all these intercurrent events will be based on a treatment policy approach; specifically, the effects estimated will be based on initial randomized treatment arm regardless of whether the participant had experienced an intercurrent event. If possible, data will continue to be collected after the occurrence of the intercurrent event, until the participant either completes the study or withdraws from the study before completion.

4.1.5. Missing Data Handling Rules

Unless otherwise stated the following rules will be applied to all Primary and Secondary endpoints:

- Missing data can occur due to study withdrawal or participants lost to follow-up before the completion of the study or due to intermittent missing values (*i.e.* data between two non-missing assessments).
- Missing data will be imputed under a missing at random (MAR) assumption using a multiple imputation (MI) model, unless otherwise specified. The MI model will include covariates; treatment, clinical status at baseline, sex and age group and baseline of the variable of interest (if appropriate). More details will be provided in [Appendix 2](#).

4.1.6. Examination of Covariates, Other Strata and Subgroups

4.1.6.1. Covariates and Other Strata

The list of covariates and other strata may be used in descriptive summaries and statistical analyses, some of which may also be used for subgroup analyses. Additional covariates and other strata of clinical interest may also be considered.

- If the number of participants is small within a category of a covariate, then the covariate categories may be refined prior to unblinding the trial.
- If the category cannot be refined further, then the covariate may be included as a continuous measure.

Category	Details
Strata	Clinical status at baseline, Sex (Male or Female)
Covariates	Treatment, Clinical Status at Baseline, Sex, Age (as continuous), baseline of the variable of interest (if appropriate).

4.1.6.2. Examination of Subgroups

The list of subgroups may be used in descriptive summaries and statistical analyses. Additional subgroups of clinical interest may also be considered.

- If there are less than 10 participants within a subgroup, then the subgroup categories may be refined prior to unblinding the trial.
- If the category cannot be refined further, then descriptive rather than statistical comparisons may be performed for the subgroup.

Subgroup	Categories
Sex	
 • Male • Female
Clinical status at baseline	
 • 5 (Hospitalized, high-flow oxygen ($\geq 15\text{L}/\text{min}$), CPAP, BiPAP, non-invasive ventilation) • 6 (Hospitalized, intubation and mechanical ventilation)
Strata at baseline	
 • Clinical Status 5 (Hospitalized, high-flow oxygen ($\geq 15\text{L}/\text{min}$), CPAP, BiPAP, non-invasive ventilation) and Male • Clinical Status 5 (Hospitalized, high-flow oxygen ($\geq 15\text{L}/\text{min}$), CPAP, BiPAP, non-invasive ventilation) and Female • Clinical Status 6 (Hospitalized, intubation and mechanical ventilation) and Male • Clinical Status 6 (Hospitalized, intubation and mechanical ventilation) and Female
Age Group	
 • 70 - < 80 years • ≥ 80 years
ICU Status at Baseline	
 • In ICU on IMV¹ • In ICU not on IMV • Not in ICU and Not on IMV

1. Subjects on Invasive Mechanical Ventilation (IMV) but not in ICU will be classified as in ICU on MV

4.2. Primary Endpoint(s) Analyses

4.2.1. Definition of Endpoint(s)

Participants are free of respiratory failure if they are in category 1, 2, 3 or 4 from the GlaxoSmithKline (GSK) modified ordinal scale adapted from World Health Organization (WHO, 2020) scale 2020 (See [Table 2](#) - Clinical Status using Ordinal Scale). Missing data prior to study withdrawal will be derived using ventilation data as described in [Section 6.3.2](#).

Participants will meet the endpoint if they are alive and free of respiratory failure at Day 28. As participants may be discharged from the investigator site prior to Day 28, analysis windows will be used to define the endpoint as described in [Section 6.3.1](#).

Table 2 Clinical Status using Ordinal Scale**Ordinal Scale (GSK modified version, adapted from WHO, 2020 version)**

CCCCI - This section contained Clinical Outcome Assessment data collection questionnaires or indices, which are protected by third party copyright laws and therefore have been excluded.

4.2.2. Main Analytical Approach

The primary endpoint will be summarized using counts and proportions of the number of participants alive and free of respiratory failure and will be analysed using a logistic regression model, adjusting for treatment, clinical status at baseline, sex and age as a continuous variable. The outcome of the model is an odds ratio for the treatment effect, a confidence interval and p-value for the odds of a difference in the proportion of participants alive and free of respiratory failure at Day 28, where an odds ratio >1 indicates improvement. The corresponding difference in proportion and confidence interval will be calculated [Ge, 2011].

In addition, unadjusted relative risks and risk differences will be calculated in addition to the adjusted odds ratios. These will be presented with 95% Wald confidence intervals. Any endpoint where an odds ratio/hazard ratio above 1 indicates improvement of otilimab over placebo, the inverse odds ratio/hazard ratio/relative risk will also be presented.

In addition, the following will be produced:

- A table and stacked bar chart of the proportion of participants in each category of the clinical status at each visit.
- a shift table from baseline to the clinical status at Day 4, 7, 14, 28, 42 and 60 including a row for improvement (defined as moving from a higher category to a lower category).

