8.2. Sample Size Determination

Otilimab and placebo will be randomized in a 1:1 ratio.

Part 1

The study will utilize a group sequential design, using a Lan-DeMets alpha-spending function to control the type I error with four interim analyses for futility, two early in the study where futility alone will be assessed, using Pocock analogue rules; and two for efficacy, at later times in the study and at the same time as futility, using the O'Brien-Fleming analogue rules [Lan, 1983]. A sample size of 800 participants will provide approximately 90% power to detect a difference of 12% in the proportion of participants alive and free of respiratory failure at a one-sided 2.5% significance level and an assumed placebo response rate of 45%. The minimal detectable effect for this design is 7%.

Full details of the decision criteria and interim analysis plan will be given in the IDMC charter and analysis plan.

The assumed placebo response is based on data from recent publications of studies of patients with severe pulmonary COVID-19 related disease [Sanofi, 2020].

Part 2

A sample size of 346 participants will provide approximately 80% power to detect a difference of 15% in the proportion of participants alive and free of respiratory failure at a one-sided 2.5% significance level and an assumed placebo response rate of 45%. The minimal detectable effect for this design is 10.6%.

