5. SAMPLE SIZE DETERMINATION

For Part 2:

A sample size of 346 participants will provide approximately 80% power to detect a difference of 15% in the proportion of participants alive and free of respiratory failure at a one-sided 2.5% significance level and an assumed placebo response rate of 45%. The minimal detectable effect for this design this design is 10.6%.

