6.3.2. Derived and Transformed Efficacy Data

6.3.2.1. Ventilation Status

Ventilation status as shown below, will be derived for Days 1-60 based on the log-based collection (start and end dates/time).

Code	Decode
1	None
2	Low flow oxygen therapy
3	High-flow oxygen therapy (>= 15 L/min)
4	Non-invasive mechanical ventilation
5	Invasive mechanical ventilation
6	Death
99	Other

Ventilation status at baseline is defined as the ventilation status at the time of dosing, if no ventilation is recorded then the last ventilation use will be assigned to baseline. If multiple ventilation types are being used at the start of baseline the worst case is assumed.

For post-baseline the worst-case ventilation on a day will be used, Other will only be considered worst-case if no other ventilation is recorded.

Ventilation statuses with missing end-dates will be assumed ongoing.

Ventilation status will only be missing after last contact for subjects who have withdrawn from the trial, such that participants with no open ventilation logs will be assumed to have Ventilation=None.

Other will not be included in figures

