6.4.3. Demographic and Baseline Characteristics

The demographic characteristics baseline disease characteristics, and randomization stratification will be summarized. Demographic characteristics include age, age group, age subgroup, race, ethnicity, sex, baseline body weight, height, and BMI. An additional summary of race (American Indian or Alaskan Native, Asian, Black or African American, Native Hawaiian or Other Pacific Islander, White, and Mixed Race) and racial combinations will be provided.

Baseline disease characteristics include ICU status, ventilation status and clinical status at baseline. Randomization strata include sex, clinical status at baseline, and combination of sex and clinical status at baseline.

An additional summary of age ranges using the EMA clinical trial results disclosure requirement categories will be produced.

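### Part 2 primary model: respiratory severity enters only as randomised category 5 versus 6, although support at dosing is already derived; splitting category 5 is an optional, low-cost gain of about 0 to 3 power points

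*SAP*

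**What the plan says.** SAP 4.2.2 states that the primary endpoint "will be analysed using a logistic regression model, adjusting for treatment, clinical status at baseline, sex and age as a continuous variable". Section 4.1.1 bases covariate adjustment on the randomised strata when these disagree with the eCRF. Section 4.1.6.2 shows what clinical status contains: level 5 is high-flow oxygen at 15 L/min or more, CPAP, BiPAP and NIV together; level 6 is intubation with mechanical ventilation. Protocol 4.1.2.2 targets no more than about 40% of Part 2 participants in category 6.

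A finer variable is derived elsewhere. SAP 6.3.2.1 says "Ventilation status at baseline is defined as the ventilation status at the time of dosing", takes the worst case when several types are in use, and gives high-flow oxygen code 3 and NIV code 4. Section 6.4.3 tabulates it: "Baseline disease characteristics include ICU status, ventilation status and clinical status at baseline". It is absent from the covariate lists in 4.1.1, 4.1.5 and 4.1.6.1, and from Table 4 in 6.2.1, which refers back to 4.1.6.1. Section 4.1.6.1 allows further covariates to be considered but names none.

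Table 3 (SAP 4.8) explains that continuous age was added because it should make the estimates more precise. No such step is taken for respiratory support.

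**The concern.** The primary response is being in categories 1 to 4 at Day 28, that is, alive and off high-flow oxygen, NIV and invasive ventilation. Support at dosing is the baseline state of the same quantity. If participants on NIV respond less often than those on high-flow oxygen, a model that treats all of category 5 alike leaves explainable variation in the error. The variable is fixed before blinded dosing, is already collected, and fits the sponsor's own reason for adding age. What is at stake is some power for the primary test and some precision of the risk difference. Bias and type I error are not at stake.

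**Working it through.** **Inputs from the documents.** "A sample size of 346 participants will provide approximately 80% power to detect a difference of 15" percentage points, "at a one-sided 2.5% significance level and an assumed placebo response rate of 45"% (SAP 5). The analysis is "conducted using a two-sided test at the 5% significance level" (SAP 2), which has the same critical value, 1.96. "Otilimab and placebo will be randomized in a 1:1 ratio" (Protocol 8.2).

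**Step 1: reproduce the design.** With p1 = 0.45, p2 = 0.60 and mean 0.525:

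n per arm = [1.96 × √(2 × 0.525 × 0.475) + 0.8416 × √(0.45 × 0.55 + 0.60 × 0.40)]² / 0.15² = (1.384 + 0.588)² / 0.0225 = 172.8, so 173 per arm and 346 in total. Power at 173 per arm is 80.05%. The minimal detectable effect comes out at about 10.5% (stated 10.6%). The plan's figure reproduces as an unadjusted two-proportion test.

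**Step 2: closed-form gain.** Assumptions, none of which is in the documents: response gap between categories 5 and 6 of 30 points; category 5 share c = 60% to 90%; NIV share of category 5 s = 30% to 50%; high-flow versus NIV gap d = 10, 20 or 30 points.

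- Total outcome variance: 0.525 × 0.475 = 0.2494.
- Explained by 5 versus 6: c(1 − c) × 0.30².
- Further explained by the split: c × s(1 − s) × d².
- Incremental R² = split variance / (total − variance explained by 5 versus 6).
- Equivalent extra participants = 346 × [1/(1 − R²) − 1].

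Example with c = 0.6, s = 0.5, d = 0.20: 5 versus 6 explains 0.0216 and the split 0.0060. R² = 0.0060/(0.2494 − 0.0216) = 0.026, worth 9.4 participants. Effective n per arm is 173/(1 − 0.0216/0.2494) = 189.4 without the split (power 83.5%) and 173/(1 − 0.0276/0.2494) = 194.5 with it (84.5%).

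| High-flow vs NIV gap | Power gain (points) | Equivalent participants |
|---|---|---|
| 10 | 0.2 to 0.4 | about 2 to 3 |
| 20 | 0.8 to 1.5 | about 8 to 13 |
| 30 | 1.8 to 3.3 | about 18 to 32 |

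**Step 3: simulation of the logistic Wald test.** 346 participants, 10,000 trials per row, marginal response 45% versus 60%, a common odds ratio across support levels, and sex and age in the model but given no effect. All three models were fitted to the same simulated trials.

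| c | s | Gap | Unadjusted | SAP model | SAP model + split |
|---|---|---|---|---|---|
| 0.60 | 0.5 | 0 | 79.8% | 84.2% | 84.0% |
| 0.60 | 0.5 | 10 | 79.2% | 83.5% | 83.4% |
| 0.60 | 0.5 | 20 | 78.7% | 82.7% | 83.7% |
| 0.60 | 0.5 | 30 | 78.6% | 82.9% | 84.8% |
| 0.60 | 0.3 | 20 | 79.4% | 83.5% | 84.4% |
| 0.75 | 0.5 | 20 | 79.6% | 82.6% | 83.8% |
| 0.75 | 0.5 | 30 | 78.9% | 82.6% | 85.2% |

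The Monte Carlo standard error of a single power is √(0.83 × 0.17/10,000), about 0.4 points. The two approaches agree: essentially nothing at a gap of 10 or less, about 1 point at 20, about 2 to 3 at 30. With no gap, the extra term costs about 0.1 points. The existing category adjustment already adds about 3 to 4 points over the unadjusted test, which is more than the split adds in any row.

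**Step 4: where the gain appears.** In logistic regression a prognostic covariate raises power but does not narrow the standard error of the log odds ratio. It moves the conditional odds ratio. For the same 45% versus 60%, the within-level log odds ratio is 0.667 with no gap and 0.699 with a 30-point gap (c = 0.6, s = 0.5), an odds ratio of 1.95 versus 2.01. The precision gain is on the standardised risk difference, which SAP 4.2.2 also reports and Table 1 lists as a summary measure of the primary estimand.

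**The case against.** The strongest objection is that the prognostic gap is nowhere in the documents. The code order in 6.3.2.1 serves a rule for choosing the worst case on a day; it is not evidence of outcome, and code 99 (other) plainly is not the worst state. Standard of care follows institutional protocols, so high-flow oxygen versus CPAP may partly reflect site habit. This stands, and it is why the size is given as a range that starts at zero.

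The change is also more than one word in a formula. Protocol 4.1.2.2 allows dosing after a change of status since randomisation, so support at dosing can disagree with the stratum. A full three-level ventilation factor would nearly duplicate category 6. The ordinal imputation in 6.2.1 already expects separation. These points stand too; they call for a single indicator with explicit coding rules.

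Three stronger readings are tempting and are not supported:

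- A reader might infer that category is the only adjustment. The model also has sex and continuous age.
- A reader might infer that the analysis is left at a bare 80%. That figure belongs to the unadjusted calculation; the SAP model gives about 83% to 84% in these simulations.
- A reader might infer a demonstrated loss across the secondary hierarchy. No secondary endpoint was examined here, and time to final ICU discharge is evaluated only in participants in ICU at baseline.

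**Conclusion.** The point holds as an optional efficiency improvement, not as a validity error. Respiratory severity is carried by a two-level factor whose larger level mixes support types that the SAP itself separates, and the general permission to consider further covariates does not pre-specify one. Splitting category 5 would be worth about 0 to 3 power points, or roughly 0 to 32 participants. That rests on an assumed 30-point gap between categories 5 and 6, the assumed shares above, and a high-flow versus NIV gap of 0 to 30 points. If there is no gap the cost is negligible, so the trade favours making the change. The sample size of 346 stays as it is.

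**What to change.** Before unblinding, add one indicator, NIV versus high-flow oxygen at dosing (from 6.3.2.1), to SAP 4.1.1, 4.1.6.1 and 4.2.2 and to the imputation covariates (4.1.5 and Table 4 in 6.2.1). Record the change in Table 3, since Protocol 8.4.1 does not list it. Keep the randomised category, sex and continuous age. State in advance:

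- how to code a participant whose support at dosing differs from the randomised category;
- how to code low-flow oxygen, none and other;
- that the term is dropped if cells are sparse or the imputation model does not converge.

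The cost is SAP wording, one model parameter and the coding rules. No new data are needed and the sample size does not change. The report should note that the odds ratio is then conditional on the finer severity measure.
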